#### CONFIDENTIAL

The information contained in this document is regarded as confidential, and may not be disclosed to another party unless such disclosure is required to initiate the study, to conduct study-related activities, or to comply with national, state, or local laws and regulations. Written authorization from the coordinating site and sponsor is required for disclosure otherwise.

Amended version 4.0 20220221

comparator group, we are further defining this group as an unblinded, non-randomized, control arm that includes patients who consent to participate as a control OR specimens requested from the BTBR (see revisions throughout Sections 3, 6, 7.1, 10, 11, and 13). A new schema has been added in Section 4 for the control arm. Eligibility in Section 9 has been reformatted to indicate the criteria that apply to either both arms or treatment arms only. Units for eligible lab values have been modified.

The inclusion criterion for platelets in the treatment arm has been revised to allow potential participants who received temozolomide in the past year to have lower platelets (Section 9.1). Evolocumab does not have myelotoxic side effects, so should not further lower platelets.

Revise injection window prior to surgery from 7-14 days to 4-14 days (see revisions in Study Schema in Section 4, Table 4, and throughout Sections 7 and 10) to allow for subject scheduling flexibility.

An exploratory objective has been added to assess the activity of T cells isolated from tumor specimens (Sections 6, 7.3, and 13.6).

Amended version 5.0 20220414

Biopsy is now allowed as a means to provide tissue in addition to surgical resection and debulking. Revised inclusion criterion #3 to include biopsy (Section 9.1). Revised language to be inclusive of biopsy material including reducing minimum amount of tissue collection needed to 20 mg from 50 mg. (See revisions throughout Sections 3, 6, 7, 9, 10, and 13; Study Schema Figure 1 and Figure 2, and Table 4)

## 2 LIST OF ABBREVIATIONS

AE	Adverse Event
ALT	Alanine Aminotransferase
AST	Aspartate Aminotransferase
BBB	Blood Brain Barrier
BTBR	Brain Tumor Center Biorepository
CBC	Complete Blood Count
CFSE	Carboxyfluorescein Diacetate Succinimidyl Ester
CMP	Comprehensive Metabolic Panel
CNS	Central Nervous System
CR	Complete Response
CT	Computed Tomography
CTCAE	Common Terminology Criteria for Adverse Events
CTL	Cytotoxic T-Lymphocyte
DLT	Dose Limiting Toxicity
DVT	Deep Vein Thrombosis
DSMB	Data and Safety Monitoring Board
ECOG	Eastern Cooperative Oncology Group
FACS	Fluorescence-activated cell sorting
GO	Gene ontology
H&P	History & Physical Exam
HRPP	Human Research Protections Program
ICI	Immune Checkpoint Inhibition
IDH	Isocitrate dehydrogenase
IV	Intravenously
KPS	Karnofsky Performance Status
LC-MS/MS	Liquid chromatography coupled to tandem mass spectrometry
LDL	Low-density lipoproteins
MGMT	O-6-methylguanine-DNA methyltransferase
MTD	Maximum Tolerated Dose
NCI	National Cancer Institute
ORR	Overall Response Rate
OS	Overall Survival
PBMCs	Peripheral Blood Mononuclear Cells
PCSK9i	Proprotein convertase subtilisin/kexin type 9 serine protease inhibitor
PK	Pharmacokinetics
PD	Pharmacodynamics
PD1	Programmed Death 1
PFS	Progression Free Survival
p.o.	per os/by mouth/orally
PR	Partial Response
PRTBTC	Preston Robert Tisch Brain Tumor Center
SAE	Serious Adverse Event
SD	Stable Disease
SGOT	Serum Glutamic Oxaloacetic Transaminase
SIL	Stable isotope-labeled
SPGT	Serum Glutamic Pyruvic Transaminase
STRING	Search tool from the retrieval of interactive genes/proteins
TIL	Tumor Infiltrating Lymphocyte

TME            Tumor Microenvironment  
TMZ            Temozolomide  
WBC            White Blood Cells  
WHO            World Health Organization  
XRT            Radiation therapy

## 3 PROTOCOL SYNOPSIS AND RESEARCH SUMMARY

### 3.1 Purpose

This Phase 0 surgical window of opportunity trial seeks to evaluate the pharmacokinetic (PK) and pharmacodynamic (PD) properties of an FDA-approved proprotein convertase/ kexin type 9 serine protease inhibitor (PCSK9i; Evolocumab) in patients with primary and recurrent glioma at the Preston Robert Tisch Brain Tumor Center (PRTBTC). Specifically, it will address the following objectives.

#### **Primary Objectives:**

Evaluate whether evolocumab crosses the blood brain barrier (BBB) and is measurable in the resected or biopsied tumor specimens of patients with primary and recurrent glioma.

#### **Secondary Objectives:**

1. Among patients treated with evolocumab, assess the association between serum and intratumoral levels of evolocumab in the patients treated with evolocumab.
2. Compare the PDs of evolocumab in treated patients relative to that observed in a control cohort of untreated patients. The characterization of the PD properties will include the following:
  - a. Lipid metabolism of tumor cells taken from resected or biopsied samples
  - b. Analysis of tumor cells expressing MHC-I will be performed by fluorescence-activated cell sorting (FACS)

#### **Hypotheses:**

We hypothesize that:

1. The PCSK9 inhibitor evolocumab can cross the BBB and accumulate intratumorally
2. Treatment with evolocumab induces measurable biologic effects when administered to patients with glioma.

### 3.2 Background and Significance

Glioma, specifically glioblastoma (GBM), accounts for 46.6% of primary brain tumors, affects approximately 10,996 people in the US annually , and results in a high mortality rate with a median survival ranging from 16.1 to 20.5 months for patients with newly diagnosed GBM . Despite aggressive, image-guided tumor resection , high-dose external beam radiotherapy or brachytherapy, and recent advances in anti-angiogenic  treatments and chemotherapy, patients with GBM typically live less than 15 months from the time of diagnosis . Immunotherapy has revolutionized treatment for several hard-to-treat cancers but has failed to make significant improvements in outcomes for patients with glioblastoma . This reflects the multiple and unique mechanisms of immune evasion and escape in this highly heterogeneous tumor .

Glioblastoma engenders profound local and systemic immunosuppression and is remarkably effective at inducing T cell dysfunction, posing a challenge to any immunotherapy-based approach. Through the use of a genetic screen, proprotein convertase subtilisin/kexin type 9 serine protease (PCSK9) has been identified as important in tumor escape from immune mediated rejection. PCSK9 is a secreted protein that binds to the low-density lipoprotein (LDL) receptor redirecting it to the lysosome for degradation rather than recycling to the plasma membrane. In preclinical experiments, genetic depletion of PCSK9 in murine tumor cells significantly attenuates their abilities to form tumors in a T cell dependent manner. Furthermore, PCSK9 depletion overcomes resistance to anti-programmed death 1 (PD1) immune checkpoint therapy with a high fraction of mice free of tumors and resistant to later challenges with parental tumor cells. A significant increase has also been observed in both the total numbers and diversity of T cells in the PCSK9 deficient tumors. Importantly, PCSK9 down-regulates MHC-I expression, in a manner similar to its regulation of LDL receptor .

Evolocumab is a PCSK9i with a well-established safety profile, is FDA-approved as a lipid-lowering agent, and is widely used to treat patients who have elevated levels of LDL. To explore the role of PCSK9i in glioma, we need first to confirm that Evolocumab crosses the blood brain barrier and achieves measurable concentration in human glioma. In this protocol, we will compare levels of Evolocumab in the tissue of treated patients to that observed in control subjects after we develop an assay that can measure the level of Evolocumab in resected or biopsied brain glioma tissue. This protocol uses a surgical window of opportunity approach, collecting tissue from patients undergoing procedures of their primary or recurrent glioma to characterize the pharmacokinetic and pharmacodynamics properties of PCSK9i in patients with glioma. We will initiate this trial as a first step to assess if it is worthwhile to repurpose Evolocumab as an immunotherapeutic agent for treatment of patients with glioma.

### **3.3 Design and Procedure**

A maximum of 10 patients with pathologically documented glioma (either newly diagnosed or at first progression/ recurrence) will be treated with Evolocumab in this study after providing informed consent. Patients will receive 420 mg (the maximum single dose) of Evolocumab subcutaneously into thigh, abdomen or upper arm 4-14 days prior to a surgical procedure or biopsy of their tumor. After the procedure, leftover tissue not required for histological analysis will be collected, and the level of evolocumab will be quantified using liquid chromatography coupled to tandem mass spectrometry (LC-MS/MS). At two time points, prior to injection of Evolocumab and at time of surgery or biopsy, peripheral blood will be drawn to analyze serum levels of the drug (for comparison to intratumoral). Twenty to one hundred milligrams of tumor per patient will be homogenized and normalized using a protein assay followed by reduction/alkylation and trypsin digestion. Stable isotope-labelled (SIL) peptides corresponding to evolocumab-specific peptides will be spiked into tryptic digests, and LC-MS/MS will be used for targeted quantification of the drug-derived and SIL forms of these Evolocumab-specific peptides. Calibration curves will be generated by spiking in of Evolocumab into blank matrix (tumor homogenates from the brain specimen repository) followed by targeted LC-MS/MS. Data analysis, including normalization to SIL standards and fitting of data to the calibration curve will be performed in Skyline as previously described. If necessary, an immunoprecipitation step using Protein A/G agarose will be utilized to enrich for immunoglobulins (including evolocumab) prior to trypsin digestion and LC-MS/MS.

A contemporaneous control arm of 20 patients who undergo craniotomy (without receiving Evolocumab) will be consented to participate in this study as control subjects and prospectively observed. Although non-randomized, these specimens will provide valuable information for exploratory comparison of the evolocumab treated and evolocumab untreated tumor specimens and their immune microenvironment. If there are difficulties recruiting prospectively patients to serve as a control group, samples from the Brain Tumor Center Biorepository (BTBR) (Pro00007434) will be considered as possible control subjects.

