## 6 OBJECTIVES AND ENDPOINTS

	Objective	Endpoint	Analysis
Primary	Evaluate the pharmacokinetics (PK) of evolocumab and whether it can cross the blood brain barrier (BBB) to accumulate intratumorally in patients with primary and recurrent glioma or glioblastoma	Presence of evolocumab detected in surgical resection or biopsy samples by means of mass spectrometry	See Section 13.4
Secondary	Compare lipid metabolism of tumor cells taken from resected or biopsied samples after dose of evolocumab to resected or biopsied samples obtained from s from untreated glioma patients.	Level of lipid metabolism within the resected or biopsied tumor as assessed via fluorescence-activated cell sorting (FACS)	See Section 13.5.1
Secondary	Compare MHC-I expression on tumor cells following administration of evolocumab to samples from untreated glioma patients with tissue	Extent of MHC-I expression within the resected or biopsied tumor, as assessed by fluorescence-activated cell sorting (FACS)	See Section 13.5.1
Secondary	Among patients treated with evolocumab, describe the strength of the association between serum and intratumoral levels of evolocumab. Peripheral blood samples to be taken before administration of evolocumab and at time of surgery or biopsy.	Correlation of serum and intratumoral levels of evolocumab	See Section 13.5.2 .
Exploratory	Describe the immune characteristics of tumor cells taken from resected or biopsied samples	Sequencing characteristics as assessed by multi-omics analysis, immune infiltration, and T cell profiling	See Section 13.6
Exploratory	Assess the activity of T cells isolated from tumor specimens in patients treated with or without evolocumab	Characterization of tumor-infiltrating lymphocytes (TILs) based on flow cytometry immunostaining of TILs for expression of markers of exhaustion (e.g., PD-1, Lag3, TIM3) and activation (CD137)	See Section 13.6

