## 10 SCREENING AND ON-STUDY TESTS AND PROCEDURES

Table 4. Schedule of Events for Treatment Arm

Description	Screening (within 14 days of starting evolocumab)	Treatment Period	Active Follow-up Period

	Pre-Evolocumab Screening	Evolocumab Injection	Surgical Procedure	Post-Operative Visit
Day(s)		1	4-14	Typically ~2 weeks following surgery
General Evaluations				
Evolocumab Informed Consent	X 			
Physical Exam	X			X
Neurologic Exam	X			X
Adverse Events			Continuous 	
Laboratory Evaluations				
CBC with differential	X			X
CMP	X			X
Lipid profile	X			
Serum Pregnancy Test, if applicable	X 	X 		
Pharmacokinetic blood draws (5 mL) 		X	X*	
Tumor tissue analysis (estimated >20mg available) 			X	
Treatment				
Evolocumab		X		

\* This blood sample taken at time of surgery or biopsy so that drug level in the blood can be compared to intratumoral concentration.

**Table 4** shows the schedule of events for the treatment arm of this study, including all study-related general evaluations, laboratory evaluations, disease evaluations, and treatments. Of particular importance for this phase 1 study are the tumor sampling and pharmacokinetic blood draws to investigate evolocumab concentration profiles following agent administration. Patients who consent to participate as a control will only be asked to have the following:

- Informed consent on the control consent form
- PK blood draw prior to surgical procedure
- Tumor tissue analysis, if available

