### **13.4 Primary Objective**

The primary objective of this study is to assess whether Evolocumab crosses the blood brain barrier (BBB) and is measurable in the resected or biopsied tumor specimens of patients with primary and recurrent glioma.

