#### **13.4.1 Variable**

By means of mass spectrometry, the level of Evolocumab within the resected or biopsied brain tumor of a patient treated with one dose of Evolocumab will be assessed.

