#### **13.4.2 Statistical Hypothesis, Model, and Method of Analysis**

The level of Evolocumab within the resected or biopsied tumor will be determined for patients treated with Evolocumab, and within a cohort of resected or biopsied control patients who were not treated with Evolocumab. Either a Wilcoxon rank sum test or a two-sample t-test will compare cohorts.

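### Comparing drug in whole tumour homogenate with untreated controls can show evolocumab in the specimen, but not by itself BBB crossing, because no rule allows for residual blood

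*Combined protocol and SAP*

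**What the plan says.** **What is to be concluded.** Section 13.4 sets the primary objective: to "assess whether Evolocumab crosses the blood brain barrier (BBB) and is measurable in the resected or biopsied tumor specimens". The hypothesis in section 3.1 is that the drug "can cross the BBB and accumulate intratumorally", and section 3.2 gives the reason: "we need first to confirm that Evolocumab crosses the blood brain barrier and achieves measurable concentration in human glioma". Crossing and being measurable are thus both part of the question.

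**What is measured.** The endpoint in section 6 is "Presence of evolocumab detected in surgical resection or biopsy samples by means of mass spectrometry". Section 13.4.1 makes it quantitative: "the level of Evolocumab within the resected or biopsied brain tumor of a patient treated with one dose of Evolocumab will be assessed". Section 3.3 describes the preparation: "Twenty to one hundred milligrams of tumor per patient will be homogenized and normalized using a protein assay". Calibration uses drug spiked into blank tumour homogenate.

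**How it is analysed.** Section 13.4.2 sets treated against untreated tumours: "Either a Wilcoxon rank sum test or a two-sample t-test will compare cohorts".

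**What else is collected.** Treated patients give serum at surgery. The note to Table 4 says: "This blood sample taken at time of surgery or biopsy so that drug level in the blood can be compared to intratumoral concentration". Sections 7.3 and 10.9.3 repeat that purpose. The only analysis stated for the pair, in sections 3.6 and 13.5.2, is Spearman's correlation, with a scatterplot in 13.5.2.

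**The concern.** A homogenate contains everything in the tissue piece, including blood in its vessels and blood from the operation. Calibration against spiked homogenate gives the total amount of drug, not the compartment it came from. In a treated patient, that blood carries evolocumab. In an untreated control it carries none. The difference between cohorts is therefore drug outside the vessels plus drug in residual blood, and the comparison cannot separate the two.

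The sections on specimen handling, correlative assessments and analysis (3.3, 7.3, 10.4, 10.9.3 and 13.4 to 13.5.2) give no rinsing step, blood marker, tumour:serum ratio or criterion for concluding that the barrier was crossed. At stake is the question that section 3.2 says must be answered first. If the plan is followed as written, a low tumour level could be reported as crossing when the data cannot tell it from blood.

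**Working it through.** The plan gives no alpha, power, effect size or quantification limit, so there is no figure of its own to reproduce. The check has four steps.

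**1. Is drug circulating at surgery?** Inputs from section 5.2.2: plasma peak at 3-7 days, half-life 11-17 days. Surgery is 4-14 days after dosing. Assuming first-order decline after the peak, serum at day 14 relative to peak is 2^(-(14 - peak day)/half-life):

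- lowest: peak day 3, half-life 11 days: 2^(-11/11) = 0.50
- highest: peak day 7, half-life 17 days: 2^(-7/17) = 0.75

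Even at the latest permitted day, about 50-75% of the peak level remains.

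**2. What tumour level does blood alone produce?** With no crossing, tumour level as a share of surgery-day serum = blood fraction × (1 - haematocrit), taking tissue density as about 1 and plasma level equal to serum level. Blood fraction and haematocrit are assumptions; the documents give neither at sampling.

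| Blood in specimen | Hct 0.45 | Hct 0.40 | Hct 0.30 |
|---|---|---|---|
| 1% | 0.55% | 0.60% | 0.70% |
| 3% | 1.65% | 1.80% | 2.10% |
| 5% | 2.75% | 3.00% | 3.50% |
| 10% | 5.5% | 6.0% | 7.0% |

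The range is 0.55-7.0% of serum. At 15% blood and haematocrit 0.30 it is 0.15 × 0.70 = 10.5%.

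Whether such carry-over is detected depends on the lower limit of quantification (LLOQ). Blood alone exceeds it once the blood fraction passes LLOQ/(1 - haematocrit). For an LLOQ of 1% of serum, that is 1/0.70 = 1.43% to 1/0.55 = 1.82% blood; for 3% of serum, it is 4.29% to 5.45%.

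**3. Can the planned correlation decide?** Simulated with zero crossing, 10 treated patients, serum CV 50%, blood-fraction CV 30% or 60%, and plasma as 0.6 of blood (all assumed; 1,500 runs per setting; levels not censored at the LLOQ). Mean Spearman rho was about 0.78-0.79 with the smaller CV and 0.57-0.59 with the larger. Drug that crosses in proportion to serum would also give a positive correlation, so the sign does not distinguish the two explanations.

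**4. Does the scale matter?** Section 3.3 normalises tumour to protein; no section does so for serum. If both were expressed per mg protein (assumed serum 60-80 mg/mL, tissue 50-150 mg/g), the range in step 2 becomes 0.55% × 60/150 = 0.22% to 7.0% × 80/50 = 11.2%. A ratio can be read only if one scale is stated.

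**The case against.** The strongest reply is that this is a phase 0 study. Its endpoint is worded as presence of drug, its size was chosen for descriptive purposes (section 13.8), and the serum needed for a tumour:serum comparison is already drawn for that purpose. Some laboratory detail also lies outside the protocol: the tube type is left to the proteomics core, part of the data analysis follows a cited method, and the tissue assay is still to be developed. Rinsing or a blood correction may be specified there.

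Much of this stands. The study can still report detection, and the paired samples could support crossing if tumour levels are high enough. It is fair to say that no correction appears in this text, but not that none is planned. None of this supplies the missing criterion. Small size excuses limited precision, not a primary comparison that leaves the main rival explanation open, and the rule for the primary conclusion belongs in 13.4 wherever the bench method is written.

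A reader might also infer that any tumour level above 7% of serum must be extravascular. The documents do not support that. The figure rests on an assumed 10% blood cap and haematocrit of at least 0.30. The haemoglobin criterion in section 9.1 does not fix haematocrit at sampling: it applies within 14 days before dosing, so the value can be 14 + 14 = 28 days old at surgery, it precedes operative blood loss, and it may be met by transfusion. Nothing caps the blood in leftover operative tissue.

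**Conclusion.** The point holds and should be fixed before tumour levels are seen. A treated-versus-untreated difference supports detection of evolocumab in tumour specimens, subject to a stated LLOQ. It does not by itself show BBB crossing, and the correlation in 13.5.2 does not close the gap.

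The size is conditional: blood-only carry-over of about 0.55-7.0% of surgery-day serum for 1-10% blood and haematocrit 0.30-0.45, higher with more blood. Levels well above any plausible carry-over would still be informative.

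A reader might go further and infer that the primary test would almost always be falsely positive for crossing. The documents give no alpha, LLOQ or blood fraction, so no such rate can be claimed. In the same zero-crossing simulation, with 20 controls at zero, an LLOQ of 2% of median serum, and two-sided 0.05 assumed, the Wilcoxon test was significant in 1-9% of runs at 1% blood and 95.5-97% at 3% blood. The rate depends on the unknowns; the absence of a rule does not.

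**What to change.** 1. **Section 13.4.** State that a treated-versus-untreated difference supports only detection in the specimen, and that crossing is concluded only where the tumour level exceeds what residual blood could explain. State the LLOQ once the assay is set.
2. **Tumour:serum ratio.** Report it for each treated patient from the surgery-day serum already collected, on one stated scale, for example tumour ng/g wet weight against serum ng/mL. Compare it with one prespecified governing bound, blood fraction × (1 - haematocrit), chosen conservatively, and show other blood fractions as sensitivity analyses. A range alone cannot classify patients. Report descriptively how many are not detected, indeterminate (detected but not above the bound) and above the bound. A required count out of 10 is not proposed: it would rest on assumed exceedance rates and on independence, and a wrong blood fraction would affect all patients together.
3. **Section 13.5.2.** Label the serum-tumour correlation as uncorrected for residual blood.
4. **Supportive check.** Where usable, take blood-protein signals such as haemoglobin from the non-targeted LC-MS/MS already planned on these tumours (sections 3.6 and 13.6). Without calibration they indicate blood content only in relative terms.

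**Cost.** Items 1 and 3 are wording. Item 2 uses samples already planned plus a recorded wet weight. Item 4 uses planned data and some analysis time. No new patients, visits or draws are needed.

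The price is in interpretation. At haematocrit 0.40, a 7.0% bound requires crossing above 7.0 - 0.6 = 6.4% of serum if actual blood is 1%, or 7.0 - 1.8 = 5.2% if it is 3%. A 2.1% bound lowers these to 1.5% and 0.3%, but blood above the assumed 3% could then be read as crossing. Low positives become indeterminate, and a conservative bound can hide modest crossing; the protocol should say so.
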